#### Feasibility

This study will assess the feasibility of recruiting patients into a prospective RCT and will obtain estimates to inform the sample size and design of a future adequately powered clinical trial. Specifically, we will be assessing randomization rate as calculated by dividing the number of patients randomized by the number of eligible participants and we will record the patient follow-up rate. In addition to our prospective study, we are

currently performing a retrospective cohort study comparing patient-reported outcomes of patients who have undergone LRTI and IB over the past 2 years. We anticipate that this retrospective study will also be instrumental in informing the design and sample size of a definitive RCT.

#### Potential Pitfalls/Alternative Strategies

We are aware of several potential pitfalls which may present challenges to our study design, and we have developed alternative strategies to ensure that we achieve our aims in the event that these pitfalls occur. First, it is possible that patients will not consent to randomization into our trial at an acceptable rate. If, by 6 months into the enrollment period, we have not successfully randomized 25 patients, we are prepared to convert to a prospective cohort design. Second, it is possible that patients will not follow-up at all time points. This has not been our experience with this population; however, should this occur, we are prepared to have patients complete PROMIS questionnaires remotely and obtain all other data over the phone.

## D2 Subject Selection and Withdrawal

#### 2.a Inclusion Criteria

The study population will consist of patients aged 50 years and older who are Englishspeaking and community-dwelling. These patients will have a confirmed diagnosis of isolated thumb CMC arthritis.

#### 2.b Exclusion Criteria

Patients will not have carpal tunnel syndrome (to avoid outcome data confusion), rheumatoid/inflammatory arthritis, or a history of chronic opioid use.

#### 2.c Subject Recruitment Plans and Consent Process

The team will review patients' medical records and radiographs to determine potential participants' eligibility. The team will recruit eligible individuals during their clinic appointments using an information form outlining the benefits and relative limitations of each procedure. Patients who are interested in participating in the study will undergo initial testing at their clinic appointment, at which time they can also provide informed consent.

#### 2.d Randomization Method and Blinding

The research team will block randomize the participants into a control group (LRTI) and a comparison group (IB); block sizes will be 4, 6, and 8. The study will not be blinded.

#### 2.e Risks and Benefits

The main risks of this study are the risks of the surgical procedures themselves. These include pain, stiffness, infection, damage to surrounding structures (nerves, tendons, blood vessels), and the possibility that the surgery would not work and necessitate revision surgery. In addition to these, there may be other unknown risks, or risks that we did not anticipate, associated with being in this study.

The patient will not benefit from being in this study. However, we hope that, in the future, other people might benefit from this study because we will obtain important information regarding surgery for thumb CMC OA.

# 2.f Early Withdrawal of Subjects and When and How to Withdraw Subjects

Patients may withdraw at any time by telling the study team they are no longer interested in participating in the study or you may send in a withdrawal letter. A sample withdrawal letter can be found at https://hrpo.wustl.edu/participants/withdrawing-from-a-study/ under Withdrawing from a Research Study.

#### 2.g Data Collection and Follow-up for Withdrawn Subjects

In the event that a patient withdraws from the study, they will continue to follow-up at standard follow-up intervals as is practice for patients regardless of whether they participate in a study or not. PROMIS data will continue to be collected as is protocol for all patients presenting to Washington University clinics, but all other study-specific data will no longer be gathered.

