#### E2 Schedule of Measurements, Visits, Safety and Adverse Events

Patients will undergo the surgery to which they are randomized, either LRTI or IB, performed by one of the seven Washington University orthopaedic hand surgeons. All patients will follow-up in clinic 2 weeks, 4 weeks, 3 months, and 1 year post-operatively.

PROMIS Physical Function and Upper Extremity scores will be collected at all clinic visits on iPad as per standard protocol for all patients presenting to a Washington University Orthopaedic Surgery clinic. Thumb ROM at carpometacarpal, metacarpophalangeal, and interphalangeal joints will be collected by a member of our team at 4 weeks, 3 months, and 1 year after surgery. Visual Analog Scale Pain and Satisfaction scores will be collected by a member of our team at 2 weeks, 4 weeks, 3 months, and 1 year after surgery. Visual Analog Scale Pain and Satisfaction scores will be collected by a member of our team at 2 weeks, 4 weeks, 3 months, and 1 year post-op. Grip and pinch strength (3-point and lateral vs contralateral values and vs preoperative values) will be collected at pre-op visit and all post-op visits except the 2 week visit. Radiographic subsidence will be measured via C-arm radiographs at 3 months and 1 year post-op. Complications (mild, moderate, severe) will be recorded throughout the course of the study at all time points. Mild complications will be defined as those with minor clinical impact (i.e., scar tenderness or sensory disturbances). Moderate complications will be defined as clinically relevant with delay in patient recovery, but not severe enough to necessitate revision surgery and resolve by

12 months after surgery (i.e., mild CRPS type I, tendinitis, neuromas treated with steroid injections). Severe complications will be defined as those which result in revision surgery, pain at rest, or impaired hand function at 12 month exam (i.e., severe CRPS type I or tendinitis and neuromas that do not improve with corticosteroid injections and require surgery). We will document patient return to work/activity at each follow-up appointment.

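### Section 2.g stops collecting complications and additional surgery once a patient withdraws, although the patient still attends the clinic, so later events and some final grades are lost from the Aim 3 counts

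*Combined protocol and SAP*

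**What the plan says.** Section 2.f gives a single form of withdrawal: "Patients may withdraw at any time by telling the study team they are no longer interested in participating in the study" (a letter is the alternative). It does not separate stopping study procedures from refusing use of the clinical record.

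Section 2.g then covers what happens next. Withdrawn patients stay in routine care: "they will continue to follow-up at standard follow-up intervals". One outcome continues: "PROMIS data will continue to be collected as is protocol for all patients presenting to Washington University clinics". The rest stops: "all other study-specific data will no longer be gathered".

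Section E2, and the matching text for Aims 2 and 3 in D1, list complications among the data collected for the study: "Complications (mild, moderate, severe) will be recorded throughout the course of the study at all time points". Grading looks ahead. A moderate complication is one that needs no revision and settles within a year of surgery. For the top grade, "Severe complications will be defined as those which result in revision surgery, pain at rest", or "impaired hand function at 12 month exam".

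Section C1 makes complications and need for additional surgery an Aim 3 outcome, with the hypothesis that the arms are similar on objective outcomes. Section 2.e names among the main risks "the possibility that the surgery would not work and necessitate revision surgery". Section F2 summarizes objective outcomes by group with descriptive statistics only.

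**The concern.** A patient can leave the study but cannot undo the operation. The risk of failure and revision continues after withdrawal, and the patient is still seen by the same clinic. Read as written, 2.g lets the trial go on receiving a questionnaire from that patient while it stops recording whether the thumb needed further surgery.

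Withdrawal may well be related to outcome. The trial is unblinded (2.d), and a patient who is doing badly has more reason to leave. Events missing for that reason lower the counts and can make the arms look more alike than they are, which is the direction of the Aim 3 hypothesis. The abstract itself describes the internal brace procedure (IB) as little studied, so these counts are among the main things that a definitive trial would take from this pilot.

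**Working it through.** **Step 1: does any text exempt safety data?**
- 2.g stops everything study-specific other than PROMIS.
- D1 and E2 list complications as study data. E3 has outcomes other than PROMIS entered into REDCap by the coordinator or therapists.
- The telephone fallback under Potential Pitfalls in D1 is for missed visits, not for withdrawal.
- No section provides for chart review after withdrawal, or asks whether a complication is open when the patient leaves.

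So 2.g and the recording rule in E2 are not reconciled, and nothing restores complications after withdrawal.

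**Step 2: which events are lost?** The rule in 2.g looks forward, so timing decides.

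| Event | Kept or lost |
|---|---|
| Complication recorded before withdrawal | Kept |
| Event that prompted withdrawal, not yet recorded | Lost |
| New complication or reoperation after withdrawal | Lost |
| Grade of a mild complication | Kept; does not depend on month 12 |
| Grade of a complication already revised | Kept; severe at once |
| Moderate-or-severe grade of a complication unresolved and unrevised at withdrawal | Lost in so far as it depends on later course |

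**Step 3: how large could the effect be?** The plan has no figure of its own to reproduce on this point; it gives no complication, reoperation or withdrawal rate.

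Inputs from the documents:
- 50 patients in total (F1).
- Retention of at least 90% (C1, Aim 1). The target is still met with 50 − 0.90 × 50 = 5 patients lost. Not all losses would be withdrawals.

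Assumptions:
- 25 operated patients per arm (the allocation ratio is not stated).
- True event counts *k* of 3, 5 or 8 in one arm.
- *m* of these events missed after withdrawal.

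Observed rate = (*k* − *m*) / 25. Each missed event moves it by 1/25 = 4 percentage points.

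| True events *k* | *m* = 0 | *m* = 1 | *m* = 2 | *m* = 3 |
|---|---|---|---|---|
| 3 | 12% | 8% | 4% | 0% |
| 5 | 20% | 16% | 12% | 8% |
| 8 | 32% | 28% | 24% | 20% |

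Dropping the withdrawn patients from the denominator changes little: for *k* = 5 the rates at *m* = 1, 2 and 3 become 4/24 = 16.7%, 3/23 = 13.0% and 2/22 = 9.1%.

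**Step 4: an expected effect instead of chosen counts.** Let *r* be the true risk, *w* the share who withdraw, and *R* the risk in withdrawn patients relative to those who stay. The risk in those who stay is *q* = *r* / (*wR* + 1 − *w*). If no event in a withdrawn patient is recorded, the observed rate over all randomized is *q*(1 − *w*). With *r* = 20% and *w* = 10% (both assumed):
- *R* = 1: *q* = 0.20/1.0 = 20.0%; observed 18.0%.
- *R* = 2: *q* = 0.20/1.1 = 18.2%; observed 16.4%.
- *R* = 3: *q* = 0.20/1.2 = 16.7%; observed 15.0%.

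The relative loss is (20 − 18)/20 = 10% to (20 − 15)/20 = 25%. For these inputs that is a worst case, because events recorded before withdrawal are in fact kept.

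**The case against.** The strongest reply has four parts.

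**The text does not name complications.** 2.g contrasts routine clinic data with study-specific data, and revision surgery is ordinarily part of the clinical record too. The sponsor may never have meant to ignore it. But the stop applies to all *other* study-specific data, complications are listed as study data, and chart data are not mentioned. Even on the kinder reading, the same clarification is needed. What does stand is that PROMIS continues because the clinic collects it anyway. A reader might infer that the plan ranks a questionnaire above safety; the documents do not support that.

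**Nothing already held is removed.** A reader might infer that a complication that drives a patient out of the study disappears from the comparison, or that any complication open at withdrawal can never be graded. Neither follows. The rule is prospective, and E2 should already have captured a complication known at a visit. Mild and already revised complications have their grade. Pain at rest may also be gradable before month 12, since the reference to the 12-month exam can be read as attaching only to hand function.

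**Stopping collection may be what the patient agreed to.** Ending research collection when someone leaves is a recognizable way to respect consent. The consent form is a separate document (J1) that was not available, and it may already cover record use. This stands, and makes the remedy conditional.

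**Little depends on these counts.** They are descriptive secondary outcomes of a feasibility pilot, and imprecise: 3 of 25 has an exact 95% interval of about 2.5% to 31%. This limits the consequence, but imprecision does not excuse an avoidable bias.

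**Conclusion.** The point holds in a limited form. Followed as written, 2.g loses new complications and reoperations after withdrawal, prompting events not yet recorded, and the moderate-or-severe grade of complications still unresolved and unrevised. The Aim 3 counts can then be too low. Unequal loss between arms is possible in an unblinded trial, but the documents hold no evidence of it.

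The size cannot be estimated from the documents. It is 4 percentage points per missed event if there are 25 per arm, and zero if no withdrawn patient has a later event. A reader might take one line of the table, such as 12% falling to 4%, as a forecast; it only restates the number of events assumed missed. Nor does the point reach the primary outcome: the randomization and retention rates, the sample size and the confidence interval in F1 do not use these data.

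The change is worth making because it is cheap and removes a possible outcome-related bias.

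**What to change.** Amend 2.g along these lines: *Withdrawal from study visits or questionnaires does not by itself end safety follow-up. Where the consent terms allow, and unless the patient refuses use of the clinical record, complications (onset, resolution and final grade) and any additional surgery on the operated thumb will be abstracted from routine clinic records through 12 months after surgery.*

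In addition:
- On the withdrawal form, record whether a complication is open and whether use of the clinical record is refused.
- In F2, state that complications and additional surgery are reported for all operated patients by assigned arm, with the number whose follow-up is incomplete.
- Check that the consent form matches, and amend it if it does not. Settle this before patients withdraw, since permission may be hard to obtain afterwards.

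The cost is one protocol paragraph, possibly a consent sentence, and chart review for a few patients who already attend the clinic. Clinical care does not change. Some patients will refuse record use, so a small gap will remain, but it will be a counted one.

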## E Study Procedures

## E1 Screening for Eligibility

The team will review patients' medical records and radiographs to determine potential participants' eligibility. The team will recruit eligible individuals during their clinic appointments using an information form outlining the benefits and relative limitations of each procedure. An initial screening REDCap data collection form has been developed and will be used to this end.

#### E2 Schedule of Measurements, Visits, Safety and Adverse Events

Patients will undergo the surgery to which they are randomized, either LRTI or IB, performed by one of the seven Washington University orthopaedic hand surgeons. All patients will follow-up in clinic 2 weeks, 4 weeks, 3 months, and 1 year post-operatively.

PROMIS Physical Function and Upper Extremity scores will be collected at all clinic visits on iPad as per standard protocol for all patients presenting to a Washington University Orthopaedic Surgery clinic. Thumb ROM at carpometacarpal, metacarpophalangeal, and interphalangeal joints will be collected by a member of our team at 4 weeks, 3 months, and 1 year after surgery. Visual Analog Scale Pain and Satisfaction scores will be collected by a member of our team at 2 weeks, 4 weeks, 3 months, and 1 year after surgery. Visual Analog Scale Pain and Satisfaction scores will be collected by a member of our team at 2 weeks, 4 weeks, 3 months, and 1 year post-op. Grip and pinch strength (3-point and lateral vs contralateral values and vs preoperative values) will be collected at pre-op visit and all post-op visits except the 2 week visit. Radiographic subsidence will be measured via C-arm radiographs at 3 months and 1 year post-op. Complications (mild, moderate, severe) will be recorded throughout the course of the study at all time points. Mild complications will be defined as those with minor clinical impact (i.e., scar tenderness or sensory disturbances). Moderate complications will be defined as clinically relevant with delay in patient recovery, but not severe enough to necessitate revision surgery and resolve by

12 months after surgery (i.e., mild CRPS type I, tendinitis, neuromas treated with steroid injections). Severe complications will be defined as those which result in revision surgery, pain at rest, or impaired hand function at 12 month exam (i.e., severe CRPS type I or tendinitis and neuromas that do not improve with corticosteroid injections and require surgery). We will document patient return to work/activity at each follow-up appointment.

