## F2 Analysis Plan and Statistical Methods

Patient demographic and clinical characteristics will be summarized using means (standard deviation, SD) or median (25th, 75th) for continuous variables and frequency (percentage) for categorical variables. The recruitment rate (95% confidence interval) will be reported as the number randomized out of the total number of participants approached to participate in the study (screened). Reasons for not wanting to participate will be summarized and reported. The effect sizes and variability of the PROMs for each group will be reported and used to determine the sample size for a larger definitive trial. Differences in PROMs between LRTI and IB at 6 weeks and 3 months will be examined using a two-sample t-test and differences in categorical outcomes (return to work/activity, yes/no, at 3 months) using Pearson chi-squared test. Changes over time will be evaluated graphically to see the trajectory of change over follow-up and for assessing critical time points to inform future study design parameters. Objective parameters will be summarized for each group using descriptive statistics. The significance level will be 0.05 for all tests due to the exploratory nature of the study.

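### VAS pain and thumb ROM have no listed pre-operative value, so the pain comparison cannot be adjusted for starting pain and the pilot cannot report the pre/post correlation

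*Combined protocol and SAP*

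**What the plan says.** The schedule appears in D1 (Study Aims 2 & 3) and again in E2.

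- **Thumb ROM:** "Thumb ROM at carpometacarpal, metacarpophalangeal, and interphalangeal joints will be collected by a member of our team at 4 weeks, 3 months", and then 1 year. No pre-operative reading is listed.
- **VAS pain and satisfaction:** "Visual Analog Scale Pain and Satisfaction scores will be collected by a member of our team at 2 weeks, 4 weeks, 3 months", and then 1 year. No pre-operative reading is listed.
- **Grip and pinch strength:** "will be collected at pre-op visit and all post-op visits except the 2 week visit". Values are to be compared with the pre-operative ones.
- **PROMIS:** "PROMIS Physical Function and Upper Extremity scores will be collected at all clinic visits on iPad as per standard protocol". This implies a pre-operative score.

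D1 and 2.c also mention some testing at enrolment: "Patients who are interested in participating in the study will undergo initial testing at their clinic appointment". Neither section says what is tested.

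On analysis, C1 counts VAS pain among the Aim 2 patient-reported outcomes. F2 compares those outcomes between arms with a two-sample t-test and uses their effect sizes and variability to size the definitive trial. F2 also says: "Changes over time will be evaluated graphically to see the trajectory of change over follow-up". Objective measures, which include ROM, are only described by group.

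**The concern.** Pain is the symptom being treated, and B1 frames the research question partly as how well each procedure relieves it. With pain recorded only after surgery, the trial can compare levels of pain but cannot show relief. The trajectory plots would begin at 2 weeks for pain and at 4 weeks for ROM.

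The larger cost falls on Aim 2. A pilot meant to inform a definitive trial should be able to report how strongly pre-operative pain predicts post-operative pain, and the SD that remains after adjustment. Those two figures decide whether the definitive trial should use baseline adjustment and how many patients that would save. Neither can be estimated from the listed schedule.

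There is also a contingency. Under Potential Pitfalls in D1, the study may become a prospective cohort if 25 patients have not been randomized by 6 months. Starting pain would then be an obvious confounder that nobody had measured.

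**Working it through.** **The plan's own figure.** The plan gives no figure on this point. Its one computed interval, in F1, is 0.404 to 0.596 for a 50% randomization rate with n = 100. The Wilson score method reproduces it (0.4038 to 0.5962). It does not depend on the ROM or VAS schedule.

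**Inputs.**
- Total n = 50 (F1). The allocation ratio is not stated. Block sizes of 4, 6 and 8 are compatible with 1:1, so 25 per arm is assumed.
- Retention of at least 90% (C1), which gives 45 patients, or 22.5 per arm on average.
- Significance level 0.05 (F2), taken as two-sided.
- Correlation r between pre- and post-operative pain: not in the documents. A range of 0.1 to 0.7 is assumed.
- All results are in units of the outcome SD.

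**Step 1: chance imbalance at baseline.** The standard error of the baseline difference is √(2/25) = 0.283 SD.
- P(|difference| > 0.3 SD) = P(|Z| > 0.3/0.283 = 1.06) = 0.289, or 29%.
- P(|difference| > 0.5 SD) = P(|Z| > 0.5/0.283 = 1.77) = 0.077, or 8%.

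**Step 2: what adjustment would gain.**
- Unadjusted half-width: t(48 df) × √(2/25) = 2.011 × 0.283 = 0.569 SD.
- ANCOVA multiplies the variance by (1 − r²). With one fewer degree of freedom and a small penalty for estimating the slope, √(1 + 1/46) = 1.011, the half-width is 2.012 × √(1 − r²) × 0.283 × 1.011.
- Equivalent n per arm, ignoring the penalty, is 25/(1 − r²).

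| Assumed r | Variance reduction (r²) | Half-width, 25 per arm | Equivalent n per arm | Half-width, 22.5 per arm |
|---|---|---|---|---|
| Unadjusted | none | 0.569 | 25.0 | 0.601 |
| 0.1 | 1% | 0.572 | 25.3 | 0.606 |
| 0.3 | 9% | 0.549 | 27.5 | 0.581 |
| 0.5 | 25% | 0.498 | 33.3 | 0.527 |
| 0.7 | 49% | 0.411 | 49.0 | 0.435 |

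At r = 0.1 the slope penalty outweighs the gain. At r = 0.3 the interval is about 3.5% narrower (0.549/0.569 = 0.965). At r = 0.5 it is about 12% narrower (0.498/0.569 = 0.875).

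**Step 3: why ANCOVA rather than a change score.** With equal SDs, a change score has variance 2(1 − r) relative to the post-operative value alone. That is 1.40 at r = 0.3, 1.00 at r = 0.5 and 0.60 at r = 0.7. A simple change score therefore loses precision unless r exceeds 0.5.

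**The case against.** **Randomization makes a baseline unnecessary.** This stands as far as bias goes. A reader might infer that the planned pain comparison is biased. It is not: the ordinary confidence interval already allows for chance imbalance. It does not stand if the study converts to a cohort, because randomization then no longer protects the comparison.

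**Imbalance is unlikely to matter.** This largely stands. Figures of 29% and 8% do not make a sizeable imbalance likely, and its effect on the outcome is diluted by the correlation. At r = 0.5, a 0.3 SD imbalance shifts the post-operative difference by about 0.5 × 0.3 = 0.15 SD.

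**ROM loses nothing in testing.** This stands. It is tempting to say that the ROM comparison loses precision, but F2 only describes objective measures, so no ROM test is weakened. What ROM loses is a starting point for change and for its trajectory.

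**A baseline may already be taken.** The testing mentioned in D1 and 2.c is undefined and could include these measures. So the supportable statement is that none is listed, not that none will exist. If they are included, the schedule should say so.

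**The planned test would ignore the baseline anyway.** True. PROMIS has an implied pre-operative score, and F2 still plans an unadjusted t-test. Collecting pre-operative pain improves precision only if the analysis changes too.

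**The definitive trial is not harmed.** This stands in part. A reader might infer that the unadjusted SD would mis-size the definitive trial. That SD is correct if the definitive trial uses a t-test and conservative if it adjusts. D1 also says a retrospective cohort will inform sample size. But neither source shows pre-operative pain for these patients, and the documents do not say that the cohort holds VAS pain.

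**Conclusion.** The concern holds as a low-cost design improvement and not as a flaw in validity. VAS pain and thumb ROM are listed only after surgery, while strength has a pre-operative value and PROMIS implies one. For VAS pain, three things are lost: adjustment for starting level, change from before surgery, and the pre/post correlation with its adjusted SD. For ROM, only the starting point is lost. Starting pain would also be an unmeasured confounder if the conversion to a cohort is triggered.

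The size depends on a correlation that the documents do not give. The gain is nil at about 0.1, slight at 0.3 and material from 0.5 upward, where 25 per arm with adjustment is worth about 33 without. These figures assume 1:1 allocation and equal SDs before and after surgery. The uncertainty about r is itself a reason for a pilot to measure it. VAS satisfaction is not part of this point, because satisfaction with surgery has no meaningful pre-operative value.

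**What to change.** 1. In D1 and E2, add VAS pain to the existing pre-operative visit, along with thumb ROM measured by the same method used after surgery.
2. In D1 and 2.c, state what the enrolment testing consists of. If it already includes these measures, list them in the schedule.
3. In F2, report the between-arm VAS pain difference adjusted for the pre-operative value (ANCOVA) with a 95% CI, together with the pre/post correlation and the adjusted SD.
4. Keep ROM descriptive, but include the pre-operative value and the change from it. Start the trajectory plots for both outcomes at the pre-operative visit.

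The change needs to be in place before the first operation, because a pre-operative value cannot be recovered later. The cost is assumed to be a few minutes per patient at a visit that already takes place, plus small edits to the case report form and F2. No new visit is needed, and the feasibility outcome is unaffected.
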